5.2.2 Secondary Endpoints

Safety

- Frequency and severity of solicited local (injection site) adverse events (AEs) for 7 days and solicited systemic AEs for 14 days after vaccination.
- Percentage of subjects with any unsolicited AEs for 28 days after vaccination.
- Percentage of subjects with serious adverse events (SAEs) throughout the trial.

Immunogenicity

- Refer to primary endpoints, but will be analyzed by dengue baseline seropositivity (MNT).

Vaccine viremia

- Incidence, duration, and level of vaccine viremia for each of the four dengue serotypes post-vaccination.

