10.4.2 Collection and Reporting of Solicited AEs

The occurrence of selected indicators of safety will be collected on diary cards by the subjects until Day 7 (solicited local reactions) or Day 14 (solicited systemic reactions) and will be recorded on the “Local and Systemic Reactions” eCRF, as appropriate. Any solicited local or systemic AE observed as continuing on trial Day 7 (local reactions) or Day 14 (systemic reactions) will be recorded as an unsolicited AE on the AE eCRF. Any solicited local or systemic AE that resolved before that time but which recurs at a later time will be recorded as an unsolicited AE on the AE eCRF.

Any solicited AE that meets any of the following criteria must be entered as an AE on the AE eCRF.

- Solicited local or systemic AEs that lead the subject to withdraw from the trial.
- Solicited local or systemic AEs that lead to the subject being withdrawn from the trial by the Investigator.
- Solicited local and systemic AEs that otherwise meet the definition of an SAE (see Section 10.1.2).

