13.1.5 Safety Analysis

All summaries of safety data will be performed using the Safety Set. The safety data will be summarized by treatment arm. For some key tables, the safety data will also be summarized by treatment arm and baseline dengue seropositivity (MNT). Full details will be provided in the SAP.

Solicited AEs

Solicited local AEs and solicited systemic AEs will be assessed by the use of diary cards for 7 days and 14 days, respectively, following vaccination (vaccination day included).

For each solicited AE, the percentage of subjects will be summarized by event severity for each day (Days 1 to 7 for local AEs and Days 1 to 14 days for systemic AEs after vaccination) and overall. A summary of the first onset of each event will also be provided. The number of days subjects experienced each event will also be summarized. For subjects with more than 1 episode of the same event, the maximum severity will be used for tabulations.

Unsolicited AEs

Unsolicited AEs will be assessed by the use of diary cards for 28 days following vaccination (vaccination day included).

Unsolicited AEs and SAEs will be coded according to MedDRA and summarized by SOC and PT. Adverse events leading to withdrawal will also be summarized.

All unsolicited AEs up to 28 days after vaccination will be included in the analyses of all AEs. For SAEs and AEs leading to subject withdrawal from the trial, any AE collected during the trial will be included.

In general, unsolicited AEs will be tabulated at each of the following levels: overall summary (subject with at least 1 AE) and by SOC and PT. Subjects reporting more than 1 occurrence for the term (level) being summarized will be counted only once. Unsolicited AEs will be summarized as follows: by PT including events with frequency greater than 2%; by SOC and PT; by SOC, PT, and severity; and by SOC, PT, and relationship to the investigational vaccine. Unless otherwise specified, unsolicited AEs will be summarized in the following 3 ways: 1) overall up to 28 days post-vaccination, 2) with onset between 1 and 14 days post-vaccination, and 3) with onset between 15 and 28 days post-vaccination.

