7.11.1 Adverse Events

Reactogenicity (Solicited adverse events [AEs])

Subjects are provided with a diary card for the recording of solicited local AEs, including injection site pain, injection site erythema, and injection site swelling, for 7 days following vaccination (day of vaccination + 6 days). Subjects are also provided with a diary card for the recording of solicited systemic AEs (fever, headache, asthenia, malaise, and myalgia) for 14 days following vaccination (day of vaccination + 13 days). Any solicited local or systemic AE observed as continuing on study Day 7 (local reactions) or Day 14 (systemic reactions) will be recorded as an unsolicited AE on the AE eCRF. Any solicited local or systemic AE that resolved before that time but which recurs at a later time will be recorded as an unsolicited AE on the AE eCRF. The details of solicited local and systemic AEs, severity of solicited safety parameters are given in [Appendix B](#).

For each solicited AE, the number of subjects and the percentage of subjects will be summarized by event severity:

- 30 minutes after study vaccination
- for each day (Days 1 to 7 after vaccination for local AEs, and Days 1 to 14 after vaccination for systemic AEs) and overall (within 7 days after vaccination for local AEs, within 14 days after vaccination for systemic AEs)
- for Day 1 to Day 3 and Day 4 to Day 7 for local AEs, Day 1 to Day 7 and Day 8 to Day 14 for systemic AEs

For subjects with more than 1 episode of the same event, the maximum severity will be used for tabulations.

For solicited systemic AEs, the number and percentage of subjects will also be summarized by relationship:

- 30 minutes after study vaccination
- Within 14 days after vaccination

Subjects will only be counted once if the subject has more than 1 episode of the same event. In the case where the subject has both related and unrelated AEs, the subject will be counted under the related category.

The number of subjects who had their first onset of each event will be provided for each day. The total number of days for each AE term will also be summarized.

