Additional subgroup analyses of AE severity will be performed by baseline seropositivity status (seropositive for at least 1 dengue serotype/seronegative for all dengue serotypes) for summaries of solicited local AEs 30 minutes after study vaccination, solicited systemic AEs 30 minutes after study vaccination, solicited local AEs within 7 days after study vaccination, and solicited systemic AEs within 14 days after study vaccination. Solicited local AEs within 7 days after study vaccination and solicited systemic AEs within 14 days after study vaccination will also be repeated by occurrence of viremia (subjects with viremia /subjects without viremia).

Additional subgroup analyses of AE relationship to study vaccine will be performed by baseline seropositivity status for summaries of solicited systemic AEs 30 minutes after study vaccination and solicited systemic AEs within 14 days after study vaccination. A summary of solicited systemic AEs within 14 days after study vaccination by relationship will also be performed by subgroup of occurrence of viremia.

For solicited AEs, missing data will be handled as follows. For each vaccine group and solicited AE, the denominator for the percentage will exclude subjects with completely missing data (i.e. subject does not have at least one recorded result of none, mild, moderate, or severe) for the solicited AE in the period being summarized.

Prolonged solicited AEs that continue beyond Day 7 (for local AEs) or Day 14 (for systemic AEs) will be identified during the blinded data review based on the question “Did the symptom continue beyond Day 7/14?” and start/end dates of the corresponding unsolicited AEs. These prolonged solicited AEs will be presented in a separate listing.

Unsolicited AEs and Serious Adverse Events (SAEs)

Any AE identified as a prolonged solicited AE will not be included in any unsolicited AE summary or listing.

Unsolicited AEs will be assessed for 28 days following vaccination (day of vaccination + 27 subsequent days). Collection of SAEs will commence from the time that the subject is vaccinated (Day 1 [Month 0]). Routine collection of SAEs and AEs leading to discontinuation from study will continue until the end of the study (Day 365 [Month 12]). Unsolicited AEs and SAEs will be coded according to MedDRA and summarized by SOC and PT.

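### Solicited AEs that continue past Day 7 (local) or Day 14 (systemic) go only to a listing, so their later severity is in no by-arm table, and the SAP does not declare this departure from the protocol

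*SAP*

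**What the plan says.** **Recording.** Under Protocol 10.4.2, a solicited AE that is continuing on Day 7 (local) or Day 14 (systemic) "will be recorded as an unsolicited AE on the AE eCRF". SAP 7.11.1 repeats this. Both documents treat in the same way a solicited AE that resolved and later came back.

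**Protocol analysis.** Protocol 13.1.5 states: "All unsolicited AEs up to 28 days after vaccination will be included in the analyses of all AEs". The related secondary safety endpoint in Protocol 5.2.2 is: "Percentage of subjects with any unsolicited AEs for 28 days after vaccination".

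**SAP analysis.** SAP 7.11.1 opens its part on unsolicited AEs and SAEs with: "Any AE identified as a prolonged solicited AE will not be included in any unsolicited AE summary or listing". Just before that, it says that prolonged events are found at the blinded data review, from a CRF question on whether the symptom went on past Day 7/14 and from the "start/end dates of the corresponding unsolicited AEs". It then says: "These prolonged solicited AEs will be presented in a separate listing".

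**Solicited tables.** Severity is tabulated by day, by sub-period, and "overall (within 7 days after vaccination for local AEs, within 14 days after vaccination for systemic AEs". The same section adds: "The total number of days for each AE term will also be summarized". It sets no last day for that summary, and neither does the matching sentence in Protocol 13.1.5.

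**Declared changes.** The log in SAP 7.13.2 notes that handling of prolonged solicited AEs was added to 7.11.1. The opening text of SAP 7.13 names only the move from randomized subjects to the safety set.

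**The concern.** A continuing reaction falls between two sets of tables. The solicited tables stop following it at Day 7 or Day 14, and the unsolicited tables, where the protocol would place the rest of it, leave it out. If it worsens after the diary window, no planned table shows that by vaccine.

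The safety objective is to describe both formulations by vaccine and baseline serostatus. Reactions that last longest are part of that description, and a listing gives no percentage per arm. There is also a traceability issue: a reader who takes the unsolicited AE percentage to follow the protocol will be reading a narrower count, with nothing in SAP 7.13 to say so.

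**Working it through.** The plan gives no figure to reproduce. The check sets the rules side by side and counts days.

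**1. Where a continuing, non-serious solicited AE is summarized**

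| Output | After Day 7/14? | Source |
|---|---|---|
| Solicited severity tables | No, they end at Day 7 (local) or Day 14 (systemic) | SAP 7.11.1 |
| Solicited systemic AEs by relationship | No, they end at Day 14 | SAP 7.11.1 |
| Unsolicited AE summaries, including severity and outcome | No, excluded | SAP 7.11.1 |
| Total days per AE term | Not stated | SAP 7.11.1; Protocol 13.1.5 |
| Separate listing | Yes, by subject, with no by-arm count | SAP 7.11.1 |

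The planned subgroup tables by serostatus and by viremia use these same outputs and so have the same gap. The solicited tables include no summary of outcome.

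**2. Length of the gap in the 28-day unsolicited period**

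- Local: Days 8 to 28, so 28 − 8 + 1 = 21 days.
- Systemic: Days 15 to 28, so 28 − 15 + 1 = 14 days.

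**3. Illustration (an invented course, not trial data)**

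A headache starts mild on Day 12, becomes severe on Day 16 and ends on Day 20.

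- Tabulated severity: mild, because only Days 12-14 are in the window.
- Days in the window: 14 − 12 + 1 = 3. Days in all: 20 − 12 + 1 = 9.
- The total-days summary could show 3 or 9, since the SAP does not say which days count.

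**4. Effect on the unsolicited AE percentage**

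A subject leaves the numerator only if every unsolicited AE recorded for that subject up to Day 28 is a prolonged solicited AE. With k such subjects in an arm of n, the percentage falls by 100 × k/n points. At the planned n = 200, one subject gives 100 × 1/200 = 0.5 points. The SAP percentage can only be equal to or lower than the one under Protocol 10.4.2 read with 13.1.5. The documents do not give k.

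**5. The trigger**

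The recording rule refers to AEs continuing *on* Day 7/14. The SAP filter asks whether the symptom continued *beyond* it. For an AE present on the last diary day and ended that day, the two may give different answers.

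**The case against.** The case for the SAP is reasonable. Protocol 10.1.1 and 10.1.2 want solicited and unsolicited AEs kept apart in the report. Counting one continuous episode in both would blur that. Protocol 10.4.2 is about which eCRF page to use, so the conflict appears only when it is read together with 13.1.5. Protocol 13.1 leaves the definition of analysis variables to the SAP. The rule is prespecified, is applied under blind, appears in the change log, and leaves the events visible by subject. All analyses are descriptive, and no decision rests on these counts.

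Much of this stands, and the exclusion can stay. It does not answer the lack of any by-arm summary of later severity, or the lack of a declared departure.

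A reader might infer more than the documents support:

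- *Duration is in no table.* Not shown: the total-days summary has no stated cap.
- *Everything after Day 7/14 is lost.* No: recurrences are recorded as unsolicited AEs and stay tabulated. Only continuing events are filtered out.
- *SAEs and withdrawals are dropped.* This rests on the joint heading alone. SAP 7.11.1 describes SAE and discontinuation summaries separately, and Protocol 13.1.5 includes any AE collected during the trial for both.
- *Events are certainly double counted.* That depends on how *on* and *beyond* are read, and the blinded review also checks dates.
- *Symptoms around Days 10-20 are of special interest.* No passage says so. Viremia sampling to Day 30 does not establish it.

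**Conclusion.** The point holds in a limited form. Under SAP 7.11.1, the severity after Day 7 (local) or Day 14 (systemic) of a continuing solicited AE is in no by-arm summary table. The unsolicited AE percentage is narrower than Protocol 10.4.2 and 13.1.5 together imply, and SAP 7.13 does not declare this as a departure. Whether duration is fully tabulated is unclear.

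The gap is 21 days for local and 14 days for systemic reactions within the 28-day period. The effect on the unsolicited percentage is 0.5 points per affected subject, assuming 200 vaccinated subjects per arm. The number affected cannot be derived, so nothing here shows that the safety profile would be materially misstated. The conflict rests on reading the protocol's recording and analysis rules together, which is the natural reading. The change is worth making because the gap follows from a stated rule and is cheap to close.

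**What to change.** Keep the 7/14-day solicited tables, which match the secondary endpoint, and keep the exclusion from unsolicited summaries. Then:

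1. Add one table to SAP 7.11.1 by vaccine received, overall and by baseline serostatus: n (%) of subjects with prolonged solicited AEs, by maximum severity as recorded on the AE eCRF, with total duration to the end date, and outcome. Protocol 10.4.1 already collects severity, dates and outcome, and Protocol 10.3 has the maximum severity of an event recorded.
2. Report that severity apart from the diary grades. Protocol Table 10.b grades erythema and swelling in mm and records fever as a temperature, whereas Protocol 10.1.1 grades AEs by function. For the same reason, and because the endpoint is fixed at 7 and 14 days, do not extend the overall solicited row.
3. State whether the total-days summary counts days after Day 7/14.
4. Confirm that the SAE, vaccine-related and discontinuation summaries retain these events. The vaccine-related summaries need this most, since the SAP describes them alongside the unsolicited ones.
5. Define the SAP filter so that *continuing on* and *continue beyond* Day 7/14 are reconciled. This can be done in the SAP without altering what sites record.
6. Declare the departure from Protocol 13.1.5 in SAP 7.13.

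The cost is one more descriptive table and a few sentences of SAP text, with no new data collection.

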7.11.2 Clinical Laboratory Evaluations

Not applicable.

7.11.3 Vital Signs

The vital signs collected in the study include systolic and diastolic blood pressure (mmHg), heart rate (bpm), body temperature ($^{\circ}\text{C}$), weight (kg) and height (cm). Measurements are taken at screening, Day 9, Day 17, and Day 30 (Month 1). Note that height and weight will only be measured at screening. BMI will be calculated based on the height and weight at screening (weight (kg)/height² (m^2)). Vital signs will be summarized descriptively by visit. The measurement parameters will be sorted or grouped in a clinically meaningful order.

Descriptive statistics (n, mean, median, SD, minimum and maximum) of vital sign parameters (observed and change from baseline) except height, weight, and BMI will be summarized by vaccine received at each visit. Only vital sign measurements at the scheduled visits will be included in the summaries.

7.12 Interim Analysis

No interim analysis will be conducted for this trial.

7.13 Changes in the Statistical Analysis Plan

Descriptive summarizations for all randomized subjects are now based on the safety set due to reasons described in Section 7.2.

7.13.1 Amendment History

Date	Amendment Number
07 Sep 2016	Initial Analysis Plan
14 Dec 2017	1

7.13.2 Summary of Changes

This section describes major changes to the SAP Version 1.0, dated 07 September 2016.

Final Version	Section	Description of Change.
2.0	General	The main rationale for this amended SAP was the Protocol Version 3.0, dated 25 April 2017 where the planned interim analysis including data up to Day 180 (Month 6) was removed. Other sections were updated for clarification and harmonization across the Dengue program.
	1.1	Administrative updates and use of eSignatures.
	5.3	Deletion of “(all subjects)” from the exploratory endpoint regarding humoral immune response for consistency to other endpoints.
	7.1.2	Imputation rules for missing severity and missing relationship to study drug were added for AEs for consistency across the Dengue program.
	7.2	The Randomized Set was introduced.
	7.2.1	Table 7.b was updated. Removal of the exclusion of single measurements as only subjects can be excluded from the Per-Protocol Set. Measurements outside of windows will not be included in the respective Per-Protocol analysis. Removal of criterion “Inadvertent unblinding of subject’s vaccine assignment to relevant site personnel and study team” as such a criterion is more relevant for pharma studies. As we have blood sample assessments for vaccine studies there is no bias here for the immunogenicity analysis results.

7.6	Clarification was added for definition of prior/concomitant medications/vaccinations.
7.10.1	Plots for seropositivity rates were added.
7.10.3	Details were added for summary of nucleotides at attenuation loci's.
7.10.5	Details added for analysis of humoral immune response data.
7.10.6	Details added for analysis of CMI data.
7.11.1	Handling of prolonged solicited AEs was added.
7.12	Update of Interim Analysis Section as no interim analysis will be conducted for this trial.
8.0	Reference Section was updated to capture all references mentioned in the SAP.

Appendix A Schedule of Trial Procedures

Visits		1	2	3	4	5	6	7	8	9	10	11	12	13 EOT ^a
Day (Month)	Screening	D1 (Month 0)	D5	D7	D9	D11	D15	D17	D21	D30 (Month 1)	D60 (Month 2)	D90 (Month 3)	D180 (Month 6)	D365 (Month 12)
Time window	-28 to -1 days		±0 days	±1 day	±2 days	±4 days	±5 days	±5 days	±10 days	±15 days				
Signed Informed Consent ^b	X													
Assessment of Eligibility Criteria ^c	X	X												
Demographics	X													
Medical History	X													
Concomitant medication ^d	X	X												X
Complete physical examination ^e	X													
Targeted physical examination ^f		X												X
Symptom-directed physical examination ^g			X	X	X	X	X	X	X	X	X	X	X	
Vital signs ^h	X				X			X		X		X		
Pregnancy test ⁱ	X	X												
Screening results		X												
Randomization		X												
Vaccine administration		X												
Injection Site Evaluation ^j		X		X										
Diary card distribution ^k		X												
Diary card collection and review				X			X			X				
Serious Adverse Events (SAEs) ^l		X	X	X	X	X	X	X	X	X	X	X	X	X

CONFIDENTIAL

Visits		1	2	3	4	5	6	7	8	9	10	11	12	13 EOT ^a
Blood Collection ^m														
Blood sample for screening dengue IgG indirect ELISA (2.5 mL)	X													
Blood sample for dengue MNT (2.5 mL)		X					X			X		X	X	X
CCI														
CCI														
CCI														
Blood sample for vaccine viremia (2.5 mL)		X	X	X	X	X	X	X	X					
Blood sample for humoral immune response (10 mL)		X								X	X	X	X	X
Blood sample for cell-mediated immunity (40 mL) ^o		X								X	X	X	X	X

Notes: ELISA=enzyme-linked immunosorbent assay; EOT=End Of Study; Ig=immunoglobulin; MNT=microneutralization test; CCI [REDACTED] 1

- (a) End of the Trial (EOT) is Day 365 (Month 12), which corresponds to 365 days following vaccination. If the subject terminates early, Day 365 procedures should be performed.
- (b) The signed informed consent of the subject needs to be obtained before performing any other study procedure.
- (c) Eligibility by review of inclusion/exclusion criteria will be documented at screening and may be re-assessed before randomization on Day 1 (Month 0).
- (d) Concomitant therapy (all medications) and vaccine history from 4 weeks prior to TDV vaccination will be collected on Day 1 (Month 0) and Day 365 (Month 12).
- (e) Physical examination including measurement of weight and height; body mass index (BMI) will be calculated automatically.
- (f) Including (but not limited to) the measurement of vital signs.
- (g) Symptom-directed examinations should assess clinically significant changes from the baseline examination.
- (h) These will include (but are not limited to) systolic blood pressure/diastolic blood pressure, heart rate and temperature.
- (i) In women of childbearing potential, urine pregnancy tests will be performed after informed consent is obtained at screening and before vaccination on Day 1 (Month 0) (within one day prior).
- (j) Injection site evaluation (pain, erythema and swelling) at 30 minutes after vaccination on Day 1 (Month 0) and on Day 7.
- (k) Diary cards will be distributed for the collection of:

CONFIDENTIAL

- Solicited local AEs until Day 7 (day of vaccination + 6 subsequent days),
- Solicited systemic AEs until Day 14 (day of vaccination + 13 subsequent days), and
- Unsolicited AEs until Day 28 (day of vaccination and + 27 subsequent days).

(l) SAEs will be reported to the Sponsor within 24 hours of the Investigator becoming aware of the event.
(m) Blood samples on Day 1 (Month 0) need to be collected before vaccination.
(n) Blood collection at screening is used to determine dengue baseline immune status (i.e., dengue naïve and pre-exposed subjects).
(o) Cell-mediated immunity (CMI) will be assessed in a subset of subjects, referred to as the CMI subset.

Appendix B Solicited Local and Systemic Adverse Events and Severity

Table 8.a Solicited Local and Systemic AEs

Local AEs (injection site)	Pain Erythema Swelling
Systemic AEs	Headache Malaise Myalgia Asthenia Fever ^(a)

(a) Fever is defined as greater than or equal to 38°C or 100.4°F regardless of method used.

Table 8.b Severity of Solicited Safety Parameters

Adverse Event	Intensity grade	Severity/Intensity
Pain at injection site	0	None
	1	Mild: No interference with daily activity
	2	Moderate: Interference with daily activity with or without treatment
	3	Severe: Prevents daily activity with or without treatment
Erythema at injection site	0	< 25 mm
	1	Mild: 25 - ≤ 50 mm
	2	Moderate: > 50 - ≤ 100 mm
	3	Severe: > 100 mm
Swelling at injection site	0	< 25 mm
	1	Mild: 25 - ≤ 50 mm
	2	Moderate: > 50 - ≤ 100 mm
	3	Severe: > 100 mm
Headache	0	None
	1	Mild: No interference with daily activity
	2	Moderate: Interference with daily activity with or without treatment
	3	Severe: Prevents normal daily activity with or without treatment
Asthenia	0	None
	1	Mild: No interference with daily activity
	2	Moderate: Interference with daily activity
	3	Severe: Prevents normal daily activity
Malaise	0	None
	1	Mild: No interference with daily activity
	2	Moderate: Interference with daily activity
	3	Severe: Prevents normal daily activity
Myalgia	0	None
	1	Mild: No interference with daily activity
	2	Moderate: Interference with daily activity
	3	Severe: Prevents normal daily activity
Fever ^(a)	NA	None
	NA	38.0-<38.5°C
	NA	38.5-<39.0°C
	NA	39.0-<39.5°C
	NA	39.5-<40.0°C
	NA	40.0-<40.5°C
	NA	40.5-<41.0°C
	NA	>=41.0°C

(a) Fever is defined as greater than or equal to 38°C or 100.4°F regardless of method taken.

NA = not applicable

CONFIDENTIAL

